9.4.7.2 Efficacy of NOX66

The following efficacy analysis will be conducted for the patients enrolled to Part 1 and Part 2 of the study. All analyses are based on the FAS. Results will be summarized by dose cohort (Part 1) or treatment arm (Part 2).

For patients with mCRPC, the change in PSA from baseline will be summarized by dose cohort (Part 1) or treatment arm (Part 2, Arm 1) assessed using samples collected on Day 1 of Cycles 1 to 5, every second cycle thereafter (i.e., Cycles 7, 9, 11 etc.), at the EOT/ED Visit and at the 6-, 9- and 12-month Follow-up visits for all patients including those that discontinued for any reason other than disease progression. A PSA response will be considered as a PSA value reduction \geq 30% from baseline at the end of Cycles 3 and 6. A PSA reduction from baseline at any time point will also be assessed as a secondary objective.

Overall response rate, defined as the percentage of patients with CR and PR, will be assessed based on change from baseline imaging (RECIST v1.1 and PCWG-3 criteria for measurable or evaluable lesions). The number and proportion of responders (CR and PR) will be presented along with the exact 95% CI (Clopper-Pearson) for the time points after Day 1. Patients are allowed to continue study treatment until disease progression, unacceptable toxicity, withdrawal of consent, start of a new anticancer therapy, withdrawal of the patient by the Investigator or termination of the study by Sponsor. Tumor imaging assessment will be continued as scheduled for the patients who are discontinued from the study for reasons other than disease progression (see Section 8.1.3). The best overall response (CR, PR, SD or progression) will be summarized.

The change in ECOG from baseline will be summarized by dose cohort (Part 1) or treatment arm (Part 2) over time. The change in pain severity and pain interference with daily activities from baseline will be summarized by dose cohort (Part 1) or treatment arm (Part 2) over time. The number and proportion of patients with a pain response (\geq 2-point reduction in pain severity and no additional opioid use) will be summarized over time along with the exact 95% CIs

(Clopper-Pearson). The time to morphine administration and/or use of analgesics together with change from baseline assessment will be calculated and summarized by dose cohort (Part 1) and treatment arm (Part 2). The number and proportion of patients with SREs and/or SSEs will be summarized at each time point and presented along with the exact 95% CI (Clopper-Pearson).

Quality of Life analyses will be performed for the Safety Analysis Set. Scale measures from the EORTC-QLQ-C30, BPI-SF, PEQ, and FACT-P (mCRPC patients only) will be summarized for all patients by dose at each on-site visit as well as the change from baseline to each on-site visit.

Survival functions will be computed for OS, PFS and PSA reduction/progression (for Part 2, Arm 1 only) using the Kaplan-Meier method. Estimates of median survival times will be presented by dose cohort (Part 1) or treatment arm (Part 2) along with 2-sided 95% CIs. The 25th and 75th percentiles and the range (minimum, maximum) will be presented as well.

Duration of response is defined as the time from the first documented overall response of CR, PR or SD to the first documented overall response of progressive disease. This will be estimated using the Kaplan-Meier method. Estimates of median survival times will be presented along with the two-sided 95% CI. The 25th and 75th percentiles and range (minimum, maximum) will also be presented.

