4.1 Overall Design

This is a Phase 1b/Phase 2a, open-label, multicenter study to determine the safety, tolerability, RP2D, efficacy, pharmacokinetics (PK) and pharmacodynamic (PD) properties of idronoxil when rectally administered as a suppository (NOX66) to patients with any solid tumor (Part 1) and patients with mCRPC, BC and NSCLC (Part 2) who are eligible for low-dose EBRT for at least one symptomatic or minimally symptomatic lesion (for the prevention of symptoms). The study will be performed in approximately 14 sites in Australia, United States (US) and Europe. The study is divided into 2 parts: Part 1 (dose escalation) and Part 2 (dose expansion). The study design allows an exploration of different doses of NOX66 (800 mg, 1200 mg, 1600 mg and 2400 mg) with safety monitoring to ensure the safety of the patients. A Safety Steering Committee (SSC) will review available safety data after the first cycle (21 days) of each dose cohort of NOX66 in Part 1 to determine the maximum tolerated dose (MTD)/RP2D.

In Cycle 1, NOX66 will be administered for 14 days followed by a 7-day rest period on a 21-day cycle. From Cycle 2 onwards, NOX66 will be administered for 7 days followed by a 7-day rest period on a 14-day cycle. Patients will continue to receive NOX66 on a cyclical basis until

disease progression, unacceptable toxicity, withdrawal of consent, start of a new anticancer therapy, withdrawal of the patient by the Investigator or termination of the study by the Sponsor.

The study population consist of patients with mCRPC, BC, NSCLC or other solid tumors who have failed at least one line of prior treatment and for whom, according to the Investigator, are eligible for low-dose EBRT for at least one symptomatic or minimally symptomatic lesion (for the prevention of symptoms).

The dose levels of EBRT will be either:

- 8 Gray (Gy) as a single fraction, or
- 20/25 Gy as 5 fractions given over 5 to 10 days.

The first EBRT dose fraction must be administered on Day 2 of Cycle 1 and the remaining dose fractions will be given between Day 3 and Day 11. The choice of one of the EBRT dose/fractions stated above will be at the discretion of the Investigator and will be determined by the clinical requirements of the patient. EBRT will be administered according to the institutional protocol.

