4.2 Scientific Rationale for Study Design

Better SOC treatments for patients with prostate cancer and patients with other solid tumors, who have exhausted treatments, are needed. Based on the positive results observed in Phase 1 clinical studies with NOX66, further investigation is warranted.

The study is divided into 2 parts: Part 1 (dose escalation) and Part 2 (dose expansion). During Part 1, four dose levels of NOX66 will be examined to determine the MTD and RP2D to be used in further clinical development of NOX66. In Part 2, the confirmed RP2D dose level will be further examined in patients with mCRPC, BC and NSCLC. Part 2 will also examine the effect of NOX66 on PSA of patients with mCRPC and the tumor response in patients with BC and NSCLC.

Radiotherapy (i.e., low-dose EBRT) will be provided to patients during this study. Low-dose EBRT is administered for the treatment of symptomatic lesions and/or to prevent asymptomatic lesions from becoming symptomatic. Low-dose EBRT (8 Gy or 20/25 Gy as 1 or 5 fractionated doses, respectively) will be administered in this study for symptom control of lesions and

prevention of signs and symptoms. The safety of the combination of NOX66 and EBRT has been tested in men with symptomatic mCRPC¹ (see IB² for details).

The starting dose, dose escalation decision points and patient population size are based on accepted methodology for Phase 1/Phase 2 studies.

In the previous study (NOX66-002A), the doses of 400 mg, 600 mg, 800 mg and 1200 mg of NOX66 were explored in combination with low-dose EBRT in patients with mCRPC. The highest dose tested in this study was 1200 mg and a total of 15 patients have been treated with this dose. There were no DLTs reported in that study. Based on the NOX66-002A study safety and efficacy data this planned study is designed to continue the dose escalation from 800 mg (400 mg BID) to 1200 mg (600 mg BID) to 1600 mg (800 mg BID) followed by 2400 mg (1200 mg BID), if tolerable.

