4.4 End of Study Definition

Once a patient completes or discontinues study drug, he/she will be followed up every 12 weeks $(\pm 2 \text{ weeks})$ after the last dose of study drug for disease progression up to 12 months, and for safety until death or the patient is lost to follow-up.

For the entire study, study completion is defined as the last visit of the last patient for any protocol related activity (last patient, last visit), including telephone contact. For individual patients, study completion is defined as the time of the patient's last data collection.

The study will finish when the last patient enrolled in Part 2 completed 6 months of treatment; all patients receiving study drug at that time will be switched to the NOX66 compassionate access program. Those patients on the compassionate access program will continue to receive NOX66 treatment until disease progression or unacceptable toxicity. These patients will be followed until death, or the patient is lost to follow-up.

5 Study Population

The study population will consist of patients with mCRPC, BC, NSCLC or other solid tumors who have failed at least one line of prior treatment and for whom, according to the Investigator, are eligible for low-dose EBRT for at least one symptomatic or minimally symptomatic lesion (for the prevention of symptoms).

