8.1.5 Clinical Outcome Assessment

A Clinical Outcome Assessment is any assessment that may be influenced by human choices, judgement or motivation and may support either direct or indirect evidence of treatment benefit. Patient reported outcome is one of these types of Clinical Outcome Assessments.

Patient reported outcome, an umbrella term referring to all outcomes and symptoms, are directly reported by the patient. Patient reported outcomes have become a significant endpoint when evaluating effectiveness of treatments in clinical trials.

Questionnaires are to be completed before any other study assessments performed on the day of the visit.

The following PRO instruments will be administered for analysis of the PRO endpoints in this study:

• European Organisation for Research and Treatment of Cancer Quality of Life Questionnaire for Cancer Patients (EORTC-QLQ-C30)

The EORTC-QLQ-C30 is a well-established PRO questionnaire developed to monitor health-related Quality of Life (QoL) outcomes among cancer patients (Section 10.6). The questionnaire assesses important functioning domains (e.g., physical, emotional, social) and common cancer symptoms (e.g., fatigue, pain, nausea, vomiting, appetite loss). The questionnaire will be completed at Screening, on Day 1 of Cycles 3 and 5, followed by every 4 cycles thereafter (e.g., Cycle 9, Cycle 13 etc.), and at the EOT/ED Visit (Table 1-1 [Parts 1 and 2]).

• Brief Pain Inventory – Short Form (BPI-SF)

Worst pain, general pain and pain's interference with daily life will be assessed during the study drug using the BPI-SF (Section 10.7). The questionnaire will be completed at Screening, on Day 1 of Cycles 3 and 5, followed by every 4 cycles thereafter (e.g., Cycle 9, Cycle 13 etc.), and at the EOT/ED Visit (Table 1-1 [Parts 1 and 2]). The BPI-SF comprises a total of 15 items measuring 2 domains: pain severity and pain interference. Items measuring pain severity (including 'worst pain') are rated on an 11-point numeric rating scale ranging from 0=No pain to 10=Pain as bad as you can imagine. All BPI-SF items are measured using a 24-hour recall period.

• Functional Assessment of Cancer Therapy – Prostate (FACT-P)

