9.2 Sample Size Determination

The primary objective of this study is to characterize the safety and tolerability of NOX66 and thereby inform the RP2D of NOX66 for future clinical studies in patients with mCRPC and other solid tumors. Hence, for Part 1 and Part 2 the number of patients has been chosen with the aim to obtain adequate safety, tolerability, safety, PK, and PD profile data while exposing as few patients as possible to the study treatments and procedures.

The sample sizes selected for this study are as follows:

- Part 1 (Dose Escalation): Up to 30 patients will be enrolled in Part 1, in cohorts of 3 to 6 patients (Dose Cohort 1) or 3 to 8 patients (Dose Cohorts 2 to 4) at each specified dose.
- Part 2 (Dose Expansion): A total of 40 patients with mCRPC will be enrolled in Arm 1 and 24 to 30 patients (12 to 15 patients per tumor type [BC and NSCLC]) will be enrolled in Arm 2. The sample sizes for Part 2 were selected to provide sufficient observations for the estimation of endpoints and to assess any signal of efficacy following NOX66 and EBRT treatment.

9.3 **Populations for Analyses**

For purposes of analysis, the following analysis sets are defined:

Population (Analysis Set)	Description
Full Analysis Set (FAS)	The FAS comprises all patients who received at least one dose of study drug.
Safety Analysis Set	The Safety Analysis Set consists of all patients who received at least one dose of study drug. In this study, the Safety Analysis Set will be the same as the FAS.
	This analysis set will be the primary analysis set for all safety endpoints.
Per Protocol Set (PPS)	The PPS consists of all patients in the FAS with $\ge 80\%$ treatment compliance and without major protocol deviations.
PK Analysis Set	The PK analysis set consists of all patients in the Safety Analysis Set and who have at least one idronoxil or metabolite plasma concentration value.
Biomarker Analysis Set	The Biomarker Analysis Set consists of all patients in the Safety Analysis Set and who have at least one plasma biomarker concentration value.

Table 9-1Populations for Analysis

Separate summaries may be provided for patients participating in Parts 1 and 2.

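### Pain response is reported on all treated patients, including those with too little baseline pain to respond; add the rate among patients with baseline pain of at least 2

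*Combined protocol and SAP*

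**What the plan says.** Section 9.4.7.2 defines pain response as at least a "2-point reduction in pain severity and no additional opioid use". The number and proportion of responders are to be summarised over time with exact Clopper-Pearson 95% intervals, by dose cohort in Part 1 and by arm in Part 2. The synopsis repeats the definition. On the analysis set, Section 9.4.7.2 says "All analyses are based on the FAS", and Section 9.3 (Table 9-1) adds: "The FAS comprises all patients who received at least one dose of study drug". Section 9.4.7.2 places the quality-of-life summaries, which include the BPI-SF, on the Safety Analysis Set. Table 9-1 says that set is the same as the FAS, so the denominator does not change.

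Section 8.1.5 describes the BPI-SF severity items as "rated on an 11-point numeric rating scale ranging from 0=No pain to 10=Pain as bad as you can imagine", with 24-hour recall.

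On who enters, Section 4.1 describes patients "eligible for low-dose EBRT for at least one symptomatic or minimally symptomatic lesion (for the prevention of symptoms". Section 4.2 adds that low-dose EBRT may also be given "to prevent asymptomatic lesions from becoming symptomatic". Section 5.1 requires eligibility for EBRT to at least one lesion and, for mCRPC, symptomatic and/or progressive disease. Neither Section 5.1 nor Section 5.2 sets a minimum pain score, and the supplied text defines no subset of patients evaluable for pain.

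**The concern.** A responder rate is usually read as the chance that treatment relieves pain in someone who has pain. Here the denominator includes patients who may have had little or none. Those patients count as non-responders whatever the treatment does, so the reported rate combines two things: how often pain falls when it can, and how many patients had enough pain at entry. Two cohorts with the same effect on pain could show different rates only because one enrolled more patients irradiated preventively. Symptomatic relief of pain is one of the outcomes on which the study is meant to give preliminary evidence (Section 2.1), so a reader will want to interpret this figure.

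**Working it through.** The plan states no expected pain-response rate and no baseline pain distribution, so there is no figure of its own to reproduce. The check has one step that needs no assumption, followed by an illustration.

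**Step 1: who can respond.** The scale has a floor of 0, so the largest possible fall equals the baseline score.

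| Baseline | Largest fall | Can reach a 2-point fall |
|---|---|---|
| 0 | 0 | No |
| 1 | 1 | No |
| 2 | 2 | Yes |
| 3 | 3 | Yes |

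If the score is a mean of items, the same holds for any baseline below 2.

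**Step 2: effect on the rate.** Let f be the share of the FAS with baseline below 2 and r the response rate among the rest. Then

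- FAS rate = (1 - f) × r
- largest possible FAS rate = 1 - f

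In a Part 1 cohort of 8 (the maximum for Cohorts 2 to 4, Section 4.1.1), two such patients cap the rate at 6/8 = 75%.

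**Step 3: size under assumed values.** Neither f nor r is in the documents. Taking r = 60%:

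| f | FAS rate = (1 - f) × 60% |
|---|---|
| 10% | 54% |
| 20% | 48% |
| 30% | 42% |
| 40% | 36% |

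Two groups with the same r but f of 10% and 40% would thus report 54% and 36%.

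**Step 4: as reported, with exact intervals.** Arm 1 plans 40 patients (Section 9.2). With f = 30%, 12 patients cannot respond and 28 can. If 17 respond (0.60 × 28 = 16.8, rounded):

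- FAS: 17/40 = 42.5% (95% CI 27.0 to 59.1)
- baseline at least 2: 17/28 = 60.7% (95% CI 40.6 to 78.5)

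With r = 50% instead:

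| f | FAS | Baseline at least 2 |
|---|---|---|
| 0% | 20/40 = 50.0% (33.8 to 66.2) | the same |
| 10% | 18/40 = 45.0% (29.3 to 61.5) | 18/36 = 50.0% (32.9 to 67.1) |
| 25% | 15/40 = 37.5% (22.7 to 54.2) | 15/30 = 50.0% (31.3 to 68.7) |
| 50% | 10/40 = 25.0% (12.7 to 41.2) | 10/20 = 50.0% (27.2 to 72.8) |

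If r is above zero, the two rates agree only when every patient starts at 2 or more.

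**The case against.** A reader might infer that the planned rate is biased low and that its interval is centred on the wrong quantity. The documents do not support that. The plan never says it estimates response among patients with pain at entry. The proportion of all treated patients who reach a 2-point fall is a legitimate descriptive quantity, and the Clopper-Pearson interval is correct for it. The restricted rate answers a different question; it does not repair an error. This part of the objection stands.

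The consequences are also limited. The pain endpoint listed in Table 3-1 is change from baseline in BPI-SF scores, and the responder rate is an additional summary. Section 9.1 plans no hypothesis test, so no decision rule or sample size depends on it. Change in pain severity is summarised separately, which gives some view of low baseline pain, though not the share below 2.

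The size is unknown. Appendix 10 says the EBRT is for symptomatic relief and pain management, and it expects over half of patients to need symptomatic EBRT to bone. That argues against assuming a large f. However, symptomatic disease is not a pain score of at least 2, and Section 4.2 also allows for asymptomatic lesions.

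Section 9.4.7.2 names the FAS but does not say whether a visit's denominator includes patients without a score at that visit. The 17/40 illustration counts all 40. Either way, a patient with a low baseline score stays in the denominator when the visit score is present.

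Finally, selecting patients on baseline pain in an uncontrolled study invites regression to the mean, which would push the restricted rate up somewhat. This also stands, and is a reason to show both rates.

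**Conclusion.** The point holds as a cheap improvement to a secondary, descriptive summary. That patients with baseline below 2 cannot respond follows from the scale and the definition alone, and nothing in the entry criteria keeps them out. The FAS rate is valid for all treated patients but is diluted by the factor 1 - f and varies with the case mix of each cohort or arm.

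The size cannot be fixed from the documents. In the worked case, with f = 30% and 17 responders both assumed, the two rates are 42.5% and 60.7%; at f = 0 there is no difference. A reader might conclude that dose cohorts or arms cannot be compared at all. That goes too far: no formal comparison is planned, and showing the two rates together with the number below 2 lets the reader see how far case mix accounts for a difference.

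**What to change.** In Section 9.4.7.2, and in the synopsis for consistency:

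1. Name the BPI-SF severity score that defines response, for example worst pain. The text now says only pain severity, and the choice decides who falls below 2.
2. Report pain response, with its exact 95% interval, among FAS patients whose baseline on that score is at least 2.
3. State how many FAS patients are excluded by that rule, by cohort and arm.
4. Keep the full-FAS rate alongside.

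This uses data already collected and costs a few lines of analysis text and one extra table row. The downsides are a smaller denominator, a wider interval (in the worked case 40.6 to 78.5 against 27.0 to 59.1), and some upward regression to the mean, which a footnote should mention.

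A separate, optional step concerns the baseline itself. Section 8.1.5 says "The questionnaire will be completed at Screening, on Day 1 of Cycles 3 and 5", so the only scheduled pre-dose score is from Screening (Days -28 to -2) and, with 24-hour recall, may not describe pain when treatment starts. A pre-dose BPI-SF on Cycle 1 Day 1, when patients are already on site, could be considered at the next amendment. It changes the schedule of activities and so needs the approvals in Section 10.1.11. The four steps above do not depend on it.

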- ^{u.} Prostate-specific antigen (PSA; patients with metastatic castration-resistant prostate cancer [mCRPC] only) will have samples collected during Screening, on Day 1 of Cycles 1 to 5, every second cycle thereafter (i.e., Cycles 7, 9, 11 etc.), at the EOT/ED Visit and at the 6-, 9- and 12-month Follow-up Visits for all patients including those who discontinue the study for any reason other than disease progression. Patients who discontinue the study drug for reasons other than disease progression will continue to have PSA evaluated until disease progression, withdrawal of consent, initiation of new anticancer therapy, the end of the 12-month follow-up period or death, whichever comes first. Patients who discontinue the study drug due to disease progression do not need to provide PSA samples during the Follow-up Visits.
- Tumor imaging and disease response assessments will be performed within 28 days prior to enrollment, every 8 weeks (\pm 7 days) from the first dose administration up to Week 26, and every 12 weeks (\pm 7 days) thereafter until disease progression, withdrawal of consent, initiation of new anticancer therapy, or death. Patients who discontinue the study drug due to any reason other than disease progression will continue to have tumor imaging and disease response assessments performed every 12 weeks (\pm 7 days) for up to 12 months after the last dose of study drug until disease progression, withdrawal of consent, initiation of new anticancer therapy, the patient is lost to follow-up or death, whichever comes first. Tumor imaging should ideally be performed during the rest period before the start of the next treatment cycle.
 - If a patient permanently discontinues the study drug due to disease progression according to RECIST v1.1 criteria, a tumor imaging and disease response assessment is not required.
 - If a patient permanently discontinues the study drug due to clinical disease progression, a tumor imaging and disease response assessment does not need to be repeated if completed ≤ 28 days of the last dose of study drug.

Patients who permanently discontinue the study drug or the follow-up period due to withdrawal of consent, Investigator to obtain tumor imaging and conduct a disease assessment at the time of the ED Visit or final Follow-up Visit if the patient agrees. A tumor imaging and disease response assessment does not need to be repeated if completed ≤ 28 days of the date of withdrawal of consent.

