7.1 Discontinuation of Study Drug

7.1.1 Safety Stopping Criteria:

It may be necessary for a patient to permanently discontinue (definitive discontinuation) study drug. If study drug is definitively discontinued, the patient will remain in the study to be evaluated for clinical observation and safety monitoring. See the SoA (Table 1-1 [Parts 1 and 2]) for data to be collected at the time of discontinuation of study drug and follow-up and for any further evaluations that need to be completed.

Patients may be discontinued from study drug in the following situations:

- Patient decision. The patient free to discontinue study drug at any time, without prejudice to further treatment.
- Any AE that in the opinion of the Investigator or Sponsor contraindicates dosing or meets the criteria for discontinuation.
- Recurrence of the same Grade 3 AE, even if recurrence is at a lower dose of study drug, with the exemption of localized skin reactions associated with drug administration which responds to topical corticosteroids.
- Unacceptable toxicity.
- Severe noncompliance with the protocol.
- Disease progression or unacceptable toxicity.
- Patient started alternative anticancer therapy including another investigational agent.
- Patient is lost to follow-up.

For patients with mCRPC, study drug will not be stopped due to rises in PSA alone. The Prostate Cancer Working Group 3 (PCWG-3) emphasized the importance of keeping patients on the study until radiographic or symptomatic progression, which better reflects the clinical course.

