8.1.1 Prostate-specific Antigen (PSA) Response and Progression (mCRPC only)

Blood for PSA assessment will be collected during Screening, on Day 1 of Cycles 1 to 5, every second cycle thereafter (i.e., Cycles 7, 9, 11 etc.), at the EOT/ED Visit and at the 6-, 9- and 12-month Follow-up Visits for all patients including those who discontinue the study for any reason other than disease progression (Table 1-1 [Parts 1 and 2]). Patients who discontinue the study drug for reasons other than disease progression will continue to have PSA evaluated until disease progression, withdrawal of consent, initiation of new anticancer therapy, the end of the 12-month follow-up period or death, whichever comes first. Patients who discontinue the study

drug due to disease progression do not need to provide PSA samples during the Follow-up Visits. PSA will be used as a blood-based biomarker for tracking and monitoring the response state during the study for mCRPC.

A PSA response will be considered as a PSA value reduction $\ge 30\%$ from baseline at the end of Cycles 3 and 6. A PSA response reduction from baseline at any time point will also be assessed as a secondary objective.

According to PCWG-3, a sequence of rising PSA values should be obtained at a minimum of 1-week intervals with a starting value of 2.0 ng/mL. PSA PFS is the time from first dose administration to PSA progression or death.

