8.1.7 Skeletal-related Events and Symptomatic Skeletal Events Assessment

Skeletal-related events and SSEs will be evaluated based on the patient's clinical history and examinations, including but not limited to incidence of fractures and pain. Assessments will be performed at each on-site study visit.

8.1.8 **Progression-free Survival**

Progression-free survival is defined as the duration of time from first dose administration to date of disease progression is objectively documented, including tumor progression, early discontinuation or death prior to data cut-off. Patients alive and progression-free at the time of data cut-off will be censored at the date last known alive. Progression-free survival will be assessed every 8 weeks (\pm 7 days) from the first dose administration up to Week 26, and every 12 weeks (\pm 7 days) thereafter until disease progression according to RECIST v1.1 criteria.

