8.1.9 Overall Survival

Overall survival is defined as time from the date of first dose administration to date of death due to any cause. Patients alive at the time of data cut-off will be censored at date last known alive.

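### Time to PSA reduction in Part 2 Arm 1 is planned as a Kaplan-Meier curve with a median, although progression, new therapy and death end PSA sampling and no event or censoring rule is given

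*Combined protocol and SAP*

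**What the plan says.** Section 9.4.7.2, and in the same terms the Synopsis (1.1), sets the method: "Survival functions will be computed for OS, PFS and PSA reduction/progression (for Part 2, Arm 1 only) using the Kaplan-Meier method". Section 9.4.7.2 continues: "Estimates of median survival times will be presented by dose cohort (Part 1) or treatment arm (Part 2) along with 2-sided 95% CIs". Quartiles and the range are added. No other method is named for time to PSA reduction.

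PSA collection is described in footnote u of the Schedule of Activities (1.3) and in 8.1.1:

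- Patients who stop the drug without progression "continue to have PSA evaluated until disease progression, withdrawal of consent, initiation of new anticancer therapy, the end of the 12-month follow-up period or death"; the earliest of these ends sampling.
- For those who stop because of progression: "Patients who discontinue the study drug due to disease progression do not need to provide PSA samples during the Follow-up Visits". They still have a sample scheduled at the end-of-treatment or early-discontinuation (EOT/ED) visit.
- A PSA rise alone does not end treatment (7.1.1): "For patients with mCRPC, study drug will not be stopped due to rises in PSA alone".

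The only PSA time-to-event endpoint with a definition is in 8.1.1: "PSA PFS is the time from first dose administration to PSA progression or death". Censoring is defined for PFS (8.1.8), "Patients alive and progression-free at the time of data cut-off will be censored at the date last known alive", and for OS (8.1.9), "Patients alive at the time of data cut-off will be censored at date last known alive". Time to PSA reduction has no event threshold, time origin or censoring rule. Section 9.4 leaves further detail to the SAP, and the supplied documents contain no SAP text on this point.

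**The concern.** Kaplan-Meier knows two states: the event has happened, or the patient is censored and assumed to have the same future chance of the event as those still followed. That suits OS and PFS, where death is an event. PSA reduction is different. A patient who dies cannot have it later. After progression or new therapy a reduction is either not measured or not attributable to study treatment. These are competing events.

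If they are treated as ordinary censoring, 1-KM estimates the response that would be seen if nobody progressed, changed therapy or died. It can never lie below the cumulative incidence, which is the proportion of treated patients who actually respond. The median is the more exposed summary: it can be finite when well under half of the patients ever respond.

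The curve would stand beside the observed PSA response proportion in a 40-patient signal-finding arm, and the two could give different impressions of activity.

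**Working it through.** **Inputs.** The plan gives no response rate, event count or median for this endpoint, so there is no figure of its own to reproduce. From the documents: cycle lengths (21 days, then 14), hence end of Cycle 3 = 21 + 2×14 = Day 49 and end of Cycle 6 = 21 + 5×14 = Day 91; Arm 1 size 40. Assumed: the proportion ever responding, *e*, and the median time to a competing event (progression, new therapy and death pooled, called the progression median below).

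**Formulas (constant hazards).** With competing hazard λp = ln 2 / median and response hazard λr = e·λp/(1−e):

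- 1-KM(t), competing events censored: 1 − exp(−λr·t)
- Cumulative incidence (CIF): e·[1 − exp(−(λr+λp)·t)]

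With no competing hazard the two coincide.

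**Central case.** e = 0.30, median 4 months: λp = 0.1733, λr = 0.3×0.1733/0.7 = 0.0743 per month. One month is 30.44 days.

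| Time | 1-KM | CIF | Gap (points) |
|---|---|---|---|
| Day 49 | 11.3% | 9.9% | 1.4 |
| Day 91 | 19.9% | 15.7% | 4.2 |
| 6 months | 36.0% | 23.2% | 12.7 |
| 12 months | 59.0% | 28.5% | 30.5 |

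The Kaplan-Meier median is ln 2 / 0.0743 = 9.3 months, although 70% never respond by construction.

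**Range.** Over e = 20–40% and progression medians of 3–6 months, the gap is 0.4–3.5 points at Day 49 and 1.3–9.6 at Day 91. At 12 months, 1-KM runs from 29% to 84% and the CIF from 16.5% to 40%.

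**Other parameterisation.** Fix the CIF at 6 months at 20–40% and let 20–60% have a competing event by then. The 6-month gap is 2.2 to 17.4 points. With 30% responding and a 50% competing risk, the Kaplan-Meier median is 8.0 months although only 42.7% would ever respond.

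**Illustration on the PSA visit days, n = 40.** Both patterns are invented; each has 14 responders (35.0%) by Day 176. Pairs are responders, competing events:

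| Day | Spread | Early |
|---|---|---|
| 22 | 2, 1 | 5, 0 |
| 36 | 3, 2 | 5, 1 |
| 50 | 2, 2 | 3, 1 |
| 64 | 2, 3 | 1, 3 |
| 92 | 2, 4 | 0, 5 |
| 120 | 1, 3 | 0, 4 |
| 148 | 1, 3 | 0, 3 |
| 176 | 1, 2 | 0, 2 |

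Spread: 1 − (38/40)(34/37)(30/32)(26/28)(21/23)(16/17)(12/13)(8/9) = 46.4%, against 35.0% observed. Early: 1 − (35/40)(30/35)(26/29)(24/25) = 35.4%, against 35.0%. Timing alone moves the gap from 11.4 points to 0.4.

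**The case against.** The strongest reply is that the plan never says these patients are censored. The rule is simply absent. If non-responders with a competing event were kept at risk to the end of follow-up, the same Kaplan-Meier procedure would return the cumulative incidence. That stands: the bias follows from the usual default, not from a stated rule. But the only method named then gives different answers depending on an unstated choice, and that needs settling.

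Second, PSA reduction/progression is a slashed phrase. The one defined PSA time-to-event endpoint is PSA PFS, which counts death as an event, so death does not compete with it and Kaplan-Meier is appropriate. This also stands. The concern applies to the reduction part only, if a separate curve is meant.

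Third, the size may be modest. The earlier mCRPC study in Section 2.1 had disease control in 10 of 15 evaluable patients at 6 months. Read as a constant hazard, that gives a progression median of 6·ln 2 / −ln(10/15) = 10.3 months; with 30% ever responding the 6-month gap is then 16.0% − 13.2% = 2.8 points. Only 15 of 25 treated patients were evaluable, so this is probably optimistic. If all 10 others had a competing event, the 6-month risk would be 15/25 = 60%, near the 65% that a 4-month median implies. Radiotherapy is given on Days 2–11 of Cycle 1, so early responses are plausible, and the gap would then be small. At the ends of Cycles 3 and 6 it is small beside the sampling error: the exact 95% CI for 12/40 is 16.6–46.5%.

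A reader might infer that the Arm 1 primary result is inflated. The documents do not support that. Section 9.4.6.2 makes the primary analysis a binary proportion with a Clopper-Pearson interval, in which no Kaplan-Meier censoring enters. A reader might also infer that sampling stops the moment a patient progresses, or that such patients can never respond. An EOT/ED sample is scheduled, a PSA rise alone does not stop the drug, and only death strictly rules out a later reduction.

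**Conclusion.** The point holds in conditional form. Kaplan-Meier with a median is the only method named for time to PSA reduction, the event and censoring are undefined, and the sampling rules create competing events. Under default censoring the direction of any error is certain (upward); its size is not. On the central assumptions it is 1.4 points at Day 49, 4.2 at Day 91, about 13 at 6 months and about 31 at 12 months. It shrinks with slower progression and nearly vanishes if responses come early. The median is the least safe output, because it can be finite when most patients never respond.

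The consequence is limited to a secondary, descriptive curve in a study without hypothesis tests (9.1). It is still worth correcting before the SAP is final, because the better method is standard and needs no new data.

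**What to change.** In Sections 9.4.7.2 and 1.1, and in the SAP:

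- Treat PSA reduction and PSA progression as separate endpoints.
- Define the PSA reduction event (for example the ≥ 30% threshold already used for PSA response), its time origin, whether the EOT/ED sample counts, and the censoring rule.
- Report its cumulative incidence by the Aalen-Johansen estimator, with progression, new anticancer therapy and death as competing events. Give 95% CIs at the ends of Cycles 3 and 6 and at later visits.
- Give no Kaplan-Meier median or quartiles for PSA reduction.
- Keep Kaplan-Meier for OS, PFS and PSA PFS.

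The cost is SAP wording and minor programming with a standard SAS procedure; no extra visits, samples or patients are needed. The displayed response curve may look less favourable.
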